9.5.2 Derivation of a new CDR

Univariate Analysis

Univariate analysis will be used to assess the association between each variable and VTE recurrence. This process will aid selection of the best variables for the multivariate analysis. The appropriate univariate technique will be chosen according to the type of data.

Multivariate Analysis

Multivariate analysis will derive one model to predict recurrent VTE. Those variables found to be strongly associated with the outcome measure ($P<0.05$), by the univariate analysis and have good inter-observer reliability ($\kappa >0.6$), will be combined using logistic regression. For continuous and ordinal variables various cut-points will be examined to determine the optimal cut-point(s). The derived CDR must be easy to use by clinicians and therefore should contain as few variables as possible. Thus, only the most informative variables will be kept in the final model. Points for the score will be attributed according to regression coefficients. The CDR will be presented in clear narrative form that does not require computation or use of statistical aids. Discrimination and calibration of the new CDR will be estimated and compared to those obtained with existed/modified CDRs using the same indices as described above.

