2.2.3 Retrospective cohort study in patients with suspected recurrent VTE

Finally, we examined potential predictors of recurrence by performing a post-hoc analysis of the REVERSE I study²⁶). Each patient in the REVERSE I cohort that had a suspected recurrent VTE during follow-up were screened for eligibility in the post-hoc analysis. Only patients with a first adjudicated suspected recurrent event were included. Potential clinical predictors of recurrent VTE consisted of clinical predictors collected at the baseline visit, information collected in physicians' clinical notes, and laboratory or imaging results at the time of the suspected recurrent VTE. The predictive value of each predictor was determined by the Chi-square test for nominal data and the unpaired 2-tailed T-test for continuous data.

In the REVERSE I cohort, out of the 646 patients who were followed, 402 patients had a suspected recurrent VTE within a mean of 20.2 months (range: 0 – 97 months) of follow-up. Of these, 376 patients were eligible for our study: 52.7% of patients were males, and the mean age was 53.1 years (\pm 17.5). Among all suspected recurrent VTE events, male gender and a positive D-dimer result at the time of suspected recurrent VTE ($p < 0.01$), as well as symptoms occurring for 10 days or less at the time of presentation ($p < 0.05$) were in favor of a recurrent VTE diagnosis. In addition, mean age was higher in patients with a confirmed recurrent VTE ($p < 0.05$). Patients who had a previous DVT confirmed were at higher risk of having a recurrence confirmed at their next suspected event than when the previous event was a proven PE ($p < 0.05$).

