9. STATISTICAL CONSIDERATIONS

9.2 Sample Size Calculation

Beyond our primary objective of validating existing CDRs, we aim at enrolling enough participants to allow the derivation of a new CDR specific to patients with suspected recurrent VTE, in order to assess whether such a new CDR could improve risk stratification in this patient population. As per accepted methodological criteria for the development of CDRs, 5-10 patients per predictor studied are required in the smallest outcome category.²⁹ At this point, we don't know if we will be able to derive a single CDR for recurrent VTE or if deriving two separate CDRs for DVT and PE will be more useful. Our sample size estimation takes this uncertainty into account. We would like to be able to use up to 10 predictors for patients with suspected DVT with a history of VTE and separately up to 10 predictors for patients with suspected PE with a history of VTE; this means that the required study sample is 100 participants with a confirmed recurrent DVT and 100 participants with confirmed recurrent PE.

In a study by [name] et al. for the diagnostic management of recurrent VTE, 26.6% of participants with suspected VTE had the diagnosis confirmed.¹¹ In another paper 40.3% of the participants with suspected PE with a history of VTE had their diagnosis confirmed.⁴ In the retrospective study that we performed as preparation for this prospective study, 29% of the participants with a suspected recurrent DVT had their recurrence confirmed and 25% of the participants with a suspected recurrent PE had the diagnosis confirmed.

For DVT, in order to be conservative, we used the percentage from our retrospective study, that is, 29%. That means that we need to enroll 345 participants with suspected recurrent DVT to have 100 participants with a confirmed recurrent DVT. For PE, using an estimate of a 25% confirmation rate we need 400 participants with a suspected recurrence to have 100 participants with confirmed PE. Total sample size for the study is estimated at 745.

If we consider that 15% of the potentially eligible participants approached for this study will be found to be ineligible or will not consent for this study, we need to screen 397 patients with a suspected recurrent DVT and 460 patients with a suspected recurrent PE for this study. Hence, to meet our total sample size of 745 we will need to screen approximately 857 for eligibility.

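### Picking each continuous predictor's best cut-point in the derivation data, then scoring from its coefficient, inflates the new rule's weights whichever order the steps take

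*Combined protocol and SAP*

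**What the plan says.** Section 9.5.2 of the combined protocol and SAP derives the new rule in stages. It begins with univariate tests: "The appropriate univariate technique will be chosen according to the type of data". Next, "Those variables found to be strongly associated with the outcome measure ($P<0.05$), by the univariate analysis" and with kappa above 0.6 go into a logistic regression. The cut-point sentence follows, under the multivariate heading: "For continuous and ordinal variables various cut-points will be examined to determine the optimal cut-point(s". The model is then reduced, in that "only the most informative variables will be kept in the final model", and "Points for the score will be attributed according to regression coefficients".

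The section does not give the number of cut-points, the range searched or the criterion for the best one. It does not say whether P<0.05 applies to the continuous variable or to the chosen split. It names no correction for the search, no shrinkage and no bootstrap, cross-validation or split sample. The new rule is compared with the existing and modified rules in the same cohort, using the same indices.

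Appendix D lists about 20 continuous items. It also records surgery, trauma, immobilization and plaster cast at 4, 8 and 12 weeks, which are alternative splits of one exposure.

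**The concern.** The best of several splits is partly best by chance. Its coefficient therefore overstates the true effect at that split, and the plan turns that coefficient into points. Items with a searchable cut gain weight from the search, whereas a plain yes/no item such as active cancer does not.

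The comparison with existing rules is also uneven. Their cut-offs were fixed in advance (Appendices A and B), while the new rule's are tuned to the cohort in which both are judged. Section 9.5.3 then applies every available stratification tool to estimate in how many participants imaging might be withheld. Overstated separation would carry into that estimate and be lost in new patients.

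**Working it through.** **Inputs from section 9.2.** The plan states that "the required study sample is 100 participants with a confirmed recurrent DVT and 100 participants with confirmed recurrent PE", and that "29% of the participants with a suspected recurrent DVT had their recurrence confirmed"; the PE rate is 25%. Reproducing its sizes: 100 / 0.29 = 344.8, rounded up to 345; 100 / 0.25 = 400; 345 + 400 = 745. These match.

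**Assumptions, where the plan is silent.** Normally distributed predictor, one binary split, univariable model, two-sided P. The main coefficient runs use nine cuts evenly spaced from the 10th to the 90th percentile. The best cut is the one with the largest 2×2 chi-square.

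**Step 1: coefficient without an entry screen.** Inflation = mean estimated log OR at the chosen cut / mean true log OR at that cut. With N = 400 and 25% events:
- OR 1.2 per SD: 0.571 / 0.314 = 1.82
- OR 1.4 per SD: 0.821 / 0.566 = 1.45

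A fixed median cut gives about 1.0 in both cases, so the search causes the bias. A check with a different true model (a step at the median, all cuts from the 10th to the 90th percentile) gave, at N = 345 / 400 / 745:
- true OR 1.5: 1.85 / 1.81 / 1.58
- true OR 2.0: 1.43 / 1.42 / 1.21

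**Step 2: coefficient after a t-test screen at P<0.05 (N = 400, nine cuts).**

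| Form of the predictor | OR/SD 1.2 | OR/SD 1.4 |
|---|---|---|
| Searched cut, after t-test screen | 2.6 | 1.6 |
| Fixed median cut, after the same screen | 1.7 | 1.1 |
| Fixed median cut, kept only if its own P<0.05 | 2.1 | 1.2 |

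The second row isolates the search for the same variable: 2.6 / 1.7 = 1.5 and 1.6 / 1.1 = 1.5. The third row stands for a binary item that passed its own screen. The run that produced it gave 2.7 and 1.55 for the searched cut, so the excess is 2.7 / 2.1 = 1.29 and 1.55 / 1.2 = 1.29. With 2.6 instead of 2.7 the first ratio is 1.24. The excess over a screened binary item is therefore about 1.25-fold (1.2 to 1.3).

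**Step 3: false entry of a pure noise variable.**
- Continuous form screened first by t-test: 4.9%, 4.9% and 5.1% at N = 345, 400 and 745.
- P<0.05 applied to the best cut: about 11–15% with 3 cuts (the lower end for quartiles, the upper for cuts at the 10th, 50th and 90th percentiles), 23–25% with 9, 34–38% with 33, and 45–47% if every cut between the 10th and 90th percentiles is tried.
- Single prespecified median cut: 4.6–5.8%.

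**Step 4: what the search does to noise that passes the t-test screen.** With nine cuts, 95–98% of such variables show P<0.05 at their best cut, against 40–47% at a fixed median cut. Their median apparent OR with nine cuts is 2.07, 2.00 and 1.64 at N = 345, 400 and 745. A later look at the dichotomised variable would remove almost none of them.

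**The case against.** The strongest reply is that the univariate screen comes first, with a test suited to the data type, and the cut-point sentence comes after it. The group's earlier predictor study used "the unpaired 2-tailed T-test for continuous data" (section 2.2.3), which supports that order. This stands. A reader might infer that the search lifts false entry well above 5%, or that several of some 20 noise variables would reach the rule. The documents do not support either as a statement of fact. On the natural order entry stays near 5%, and the higher rates hold only if the threshold is applied to the searched cut. Even then they count entries to the candidate model, before the kappa filter and the final reduction.

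A second reply is that binary items are inflated too, because they also pass a P<0.05 screen. This also stands. A reader might take the 1.8-fold and 1.4-fold figures as the excess of continuous over binary items, but against a screened binary item the excess is about 1.25-fold. Surgery is a poor example of an unaffected item, since its 4, 8 and 12-week windows could be searched as well.

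A third reply is that existing cut-offs may not carry over. Section 2.2 itself warns that calf and leg swelling overlap with post-thrombotic syndrome, and some items in Appendix D, such as saturation and CRP, have no cut-off in the documents. That limits how well any fixed cut-off will be placed. It does not justify choosing the cut-off by outcome in the same patients.

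None of these replies removes the coefficient bias, which is present under either order of steps.

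**Conclusion.** The point holds for the coefficients. In the secondary derivation of a new rule, the searched cut inflates the log OR about 1.8-fold (OR/SD 1.2) or 1.4 to 1.5-fold (OR/SD 1.4) without a screen. After a t-test screen the figures are 2.6-fold and 1.6-fold, part of which is due to the screen itself (1.7 and 1.1). These rest on nine cuts, 400 patients with 25% events and a normal predictor; the step-effect check shows less inflation if DVT and PE are pooled (N = 745).

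For false entry the finding is a gap in the plan: near 5% on one reading, about 11% to 38% on the other for 3 to 33 cuts, with nothing stated to settle it.

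The primary validation of the Wells and Geneva rules uses existing scores and is untouched, so a reader should not infer that the main objective is at risk. The change should be made before the derivation analysis.

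**What to change.** Delete the optimal cut-point search from section 9.5.2 and replace it with the following:

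1. Apply the P<0.05 screen to continuous predictors in continuous form, and fit them in the model that way (linear, or a restricted spline if needed).
2. For the point score, use cut-offs fixed before outcome data are seen: those of the existing rules where they exist, otherwise values prespecified by the investigators. Choose one of the 4, 8 and 12-week windows for each exposure under the same rule.
3. Because the screen inflates coefficients even at fixed cut-offs, bootstrap the whole selection process, shrink the coefficients before assigning points, and report optimism-corrected discrimination and calibration.

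The cost is SAP wording and some programming; no extra participants or data are needed. The apparent in-sample fit will look less favourable, and some information may be lost where a prespecified cut-off is poorly placed. Resampling alone would measure the optimism but leave the searched cut-offs in the rule, so it complements steps 1 and 2 and does not replace them.

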9.6 Secondary Outcome Analysis

9.5.1 Recalibration / minor adjustment to existing rules

Recalibration

For each existing CDR, a multivariate regression analysis including all predictors from the CDR will be conducted. The regression coefficients obtained from this model in our sample will be examined to evaluate whether changes in the points given to each predictor in the rule need to be modified in patients with a suspected recurrent VTE.

Minor adjustments

For each existing CDR, a multivariate regression analysis including all predictors from the CDR will be performed. Candidate predictors will also be included in the analysis, but keeping in the model predictors from the CDR. Should one or two candidate predictors significantly improve risk stratification, a modified score could be proposed for patients with suspected recurrent VTE. Potential improvements in classification will be assessed using the Net Reclassification Improvement and the Integrated Discrimination Improvement indices.

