9.5.3 D-dimer testing

We will estimate what the proportion of participants will be with a non-high pre-test probability (using all the possible stratification tools described above) and negative D-dimer test result and in whom imaging could potentially be withheld. We furthermore will estimate what the false negative rate will be in this proportion of participants. These proportions will be computed along with their 95% confidence intervals.

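### The new and modified decision rules are built and compared with the existing rules in the same participants, without internal validation, so on average they will look better than they are

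*Combined protocol and SAP*

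**What the plan says.** Section 9.5.2 describes a chain of steps that all depend on the outcome data. Variables pass a univariate screen at P<0.05 and an inter-observer kappa above 0.6. Several cut-points are tried for continuous and ordinal variables, and the best is kept. Then "Thus, only the most informative variables will be kept in the final model", with no algorithm named, and "Points for the score will be attributed according to regression coefficients". The result is evaluated as follows: "Discrimination and calibration of the new CDR will be estimated and compared to those obtained with existed/modified CDRs", using the indices already given for the existing rules.

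Section 9.5.1 refits each existing rule in this sample and allows additions: "Should one or two candidate predictors significantly improve risk stratification, a modified score could be proposed". Its yardstick is: "Potential improvements in classification will be assessed using the Net Reclassification Improvement and the Integrated Discrimination Improvement indices". It states no screen and no cut-point search. Section 9.5.3 then estimates the false-negative rate of a non-high probability plus a negative D-dimer "using all the possible stratification tools described above", which includes the new and modified rules.

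The study has a single cohort. The only validation planned, in section 9.5, is of the existing rules. The contents list shows no validation section that could have been lost from the public text.

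**The concern.** A rule tuned to a sample performs better in that sample than in new patients. Wells and Geneva have published points, so they carry no such advantage here. The difference between the new rule and the old ones therefore contains the new rule's optimism in full.

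Section 1.2 asks whether a new rule would improve risk stratification over the existing ones. As written, the plan answers with uncorrected figures. From overfitting alone, a real gain would be overstated, and in some settings a rule that is no better would appear better.

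The sample size offers less protection than it seems to. Section 9.2 asks for five to ten patients in the rarer outcome group for each predictor studied, but counts only the ten predictors it hopes to use, not the number that will be screened.

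**Working it through.** **The plan's own figure.** Section 9.2 takes 10 predictors × 10 events = 100 events per rule. With confirmation rates of 29% (DVT) and 25% (PE), 100/0.29 = 344.8, so 345, and 100/0.25 = 400. The total is 745, which reproduces.

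**Events per candidate.** Appendix D lists 26+15+14+25+2+3+5+3+1 = 94 items, counting an item with several time windows once. Two are constant by eligibility (inpatient/outpatient; previous DVT proximal/distal), leaving 92. Section 9.2 leaves open whether there will be one rule or two, while section 9.5.2 says "Multivariate analysis will derive one model to predict recurrent VTE", so both cases are shown.

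| Candidates screened | Separate rule (100 events) | Pooled rule (200 events) |
|---|---|---|
| 92 | 100/92 = 1.1 | 200/92 = 2.2 |
| 46 (half removed by the reliability filter and near-duplicates) | 100/46 = 2.2 | 200/46 = 4.3 |

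All four are below 5. At 5 to 10 per predictor, 100 events support 10 to 20 candidates and 200 support 20 to 40.

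**Simulation of section 9.5.2.** These assumptions are not in the documents:
- Half the candidates are binary (20% prevalence) and half normal, with latent correlation 0.3 in blocks of four.
- There are eight true predictors, with odds ratio 1.5 per unit or SD.
- Event rates are 29% (DVT), 25% (PE) and 200/745 = 26.8% (pooled).
- The procedure is a screen at P<0.05, the best of seven cut-points where searched, then backward selection at P<0.05 to at most ten variables.
- There are 200 runs per scenario, with the true value taken from 12,000 new patients.

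Optimism is the apparent minus the new-patient c-statistic:

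| Model | Candidates | No cut-point search | With search |
|---|---|---|---|
| DVT, N=345 | 14 | 0.034 | 0.066 |
| DVT, N=345 | 30 | 0.056 | 0.097 |
| DVT, N=345 | 77 (chest-only items dropped) | 0.084 | 0.130 |
| PE, N=400 | 92 | 0.089 | 0.137 |
| Pooled, N=745 | 46 | 0.029 | 0.068 |
| Pooled, N=745 | 92 | 0.046 | 0.087 |

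For scale, the sampling SD of the apparent c-statistic is about 0.03 at N=345 and 0.02 at N=745.

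**Sensitivity.**
- Re-programming the exercise gave, without search, 0.034 to 0.046 (14 candidates), 0.089 to 0.099 (77) and 0.042 to 0.050 (pooled, 92). With search it gave 0.080, 0.177 and 0.113.
- An odds ratio of 1.8 lowers the table's values to 0.037/0.085 (30), 0.061/0.112 (77) and 0.035/0.074 (pooled, 92), without/with search.
- A simulation with 94 independent candidates, a cut-point search and five or eight true predictors (log odds ratio 0.8) gave 0.115 to 0.149 for separate rules and 0.051 to 0.073 pooled. With ten pre-specified candidates, five of them true, it still gave 0.041 (DVT) and 0.048 (PE).

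**Calibration.** Without search, the slope in new patients is 0.76 (pooled, 92), 0.71 (DVT, 30) and 0.60 (DVT, 77). An unrounded fit has slope 1 in its own sample by construction.

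**Comparison with an existing rule, no search.** If the existing rule holds six of the eight true predictors, a true gain of 0.060 is reported as 0.106 (pooled, 92), and 0.034 as 0.089 (DVT, 30). If it holds all eight, the new rule is truly worse but looks better in 15% and 48% of runs.

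**Modified rule as in section 9.5.1, with no useful candidate left.** IDI is 0.031 against a true 0.004 (pooled, 92) and 0.042 against 0.003 (DVT, 30). Category-free NRI is 0.34 against 0.08 and 0.38 against 0.07. With four useful candidates left, IDI is 0.088 against 0.073 and 0.109 against 0.072.

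**False-negative rate in section 9.5.3.** Assuming D-dimer sensitivity 95%, specificity 40% and non-high as the lower half of the score, the gap is 0.2 to 0.7 patients in a stratum of about 60 (N=345) or 132 (N=745). That is below sampling error: the exact 95% interval for 1/60 is 0.04% to 8.9%.

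**Does whole-process bootstrapping work?** Apparent to corrected c-statistic, with the true value in brackets:
- No search: 0.766 to 0.732 (0.731; 14 candidates), 0.737 to 0.677 (0.683; 30), 0.746 to 0.648 (0.660; 77), 0.738 to 0.678 (0.688; pooled, 92).
- With search: 0.738 to 0.658 (0.639; 30), 0.727 to 0.645 (0.644; pooled, 92).

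**The case against.** The strongest reply is that this is a secondary, derivation-stage analysis. The protocol summary makes use of the rule conditional on later proof, and the primary analysis is untouched. That limits the severity. However, no later step is planned, and later validation would not correct the comparison that this study itself reports.

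Several points about the figures stand as cautions:
- **The 92 candidates are an upper bound.** Section 9.5.2 names no list, and the kappa filter is approximated only by halving. Optimism nevertheless remains at 14 candidates.
- **The NRI values are category-free.** The plan names no NRI type, and the rules are banded. A re-run with assumed cuts (30%, or 15% and 50%) gave a categorical NRI of 0.04 to 0.10 apparent against -0.035 to 0.008 in new patients. The direction is the same on a much smaller scale.
- **The all-eight case is a worst case.** It makes the existing rule the data-generating model. Real rules have unequal weights, and their previous-VTE item is constant or nearly so here.
- **Appendix E pulls the other way.** It excludes recurrence when the existing rule is non-high and D-dimer is negative, which favours the existing rules. This was not quantified, and the false-negative calculation ignores it.
- **The bootstrap was tested for the c-statistic only**, not for slope, NRI, IDI or the modified rule.

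None of this removes the bias from building and judging a rule in the same data.

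**Conclusion.** The concern holds. Followed as written, the plan gives a biased answer to the secondary objective of whether a new or modified rule improves on the existing ones. This is more than a missing detail, because the unmodified rules carry no matching bias. The omission and the average direction are firm.

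The size is not firm. With eight true predictors at odds ratio 1.5, c-statistic optimism is about 0.03 to 0.10 without a cut-point search and about 0.07 to 0.18 with one. It is smallest for a pooled rule or a short candidate list. That generally equals or exceeds the sampling SD of the statistic and can be as large as the gain being sought. The effect on the false-negative rate is minor, and the primary validation of the existing rules is unaffected.

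**What to change.** 1. **Main change, sections 9.5.1 and 9.5.2.** Name the selection algorithm. Repeat screening, cut-point choice, selection and point assignment in every bootstrap resample. Report optimism-corrected c-statistic, calibration slope, NRI and IDI for the new and modified rules, stating the NRI type and how points are turned into probabilities. Base any claim of improvement on the corrected difference.
2. **Section 9.5.3.** Label the false-negative rate of new and modified rules as apparent, or give a corrected value beside it.
3. **Section 9.2.** Before outcomes are seen, pre-specify a short candidate list per model, or restate events per predictor for the number actually screened. The protocol's own survey and retrospective study could supply the list. D-dimer is left out because section 9.5.3 combines it with the rule; symptom duration and previous event type are added. For a separate model: 7 site-specific + 7 general - 1 duplicate (cancer) - 1 (D-dimer) + 2 = 14, and 100/14 = 7.1 events per candidate. Pooled: 7 PE + 3 further DVT + 5 further general + 2 = 17, and 200/17 = 11.8. A short list reduces the problem but does not replace item 1.

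The cost is SAP wording and computing time, with no new data or participants. Reported performance will be lower. Residual error of up to about 0.02 in the c-statistic, in either direction, remains after correction. An interval for the corrected difference needs a further resampling layer. A corrected false-negative rate resting on one or two events is unstable, and a short list may miss a useful predictor.
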